3.2 Sample size

The sample size for this study is based on the expected prevalence of G6PD deficiency at the study site and by data requirements set by WHO PQ [15]. This requires obtaining samples from participants with a range of G6PD activity levels. The WHO PQ process defines these levels as such:

Table 2. G6PD activity thresholds

Females	
Deficient	G6PD activity < 30% of the adjusted male median
Intermediate	G6PD activity 30%-80% of the adjusted male median
Normal	G6PD activity > 80% of the adjusted male median
Males	

Deficient	G6PD activity < 30% of the adjusted male median
Normal	G6PD activity > 30% of the adjusted male median

According to the Target Product Profile (TPP), the novel POC G6PD will need to be at least 95% sensitive for detecting G6PD activity levels at 30% to 80% of normal enzyme activity. Assuming a sensitivity of 95%, with a confidence interval of 95%, and a 1% to 2% maximum marginal error, a minimum of 162 participants with deficient and intermediate G6PD activity will be needed. To account for any possible device/diagnostic failures or compromised blood samples due to insufficient blood, signs of blood degradation, or contamination, to the sample size will need to increase by 20%. In addition, to ensure there are sufficient deficient and intermediate participants in the case of a lower-than-expected enrollment rate of these two groups occurs, at least 200 participants of each group should be included in the study. This additional enriched sample will also serve to meet the requirements of the WHO PQ. Eligible adults and children aged 2 years old and above will be recruited for potential participation though diagnostic performance analysis will not be segmented based on age.

The estimated prevalence of G6PD activity at less than 30% of normal enzyme activity is 5% in Brazil [16]. In Brazil, testing a minimum of 2,000 individuals is expected to generate approximately 100 deficient and 200 intermediate individuals. These data will be combined with data from other clinical evaluation sites in Ethiopia and India. The estimated prevalence of G6PD activity at less than 30% of normal enzyme activity is 2.5% in Ethiopia and 5% in India [16]. In Ethiopia, testing a minimum of 1,500 individuals is expected to generate approximately 38 deficient and 75 intermediate individuals and in India testing a minimum of 1,000 individuals is expected to generate approximately 50 deficient and 100 intermediate individuals. By combining the data from multiple clinical sites, these studies will reach the target number of samples required by WHO PQ.

Per guidance from the WHO PQ and US FDA guidelines for usability testing, 15 purposively selected intended users of POC G6PD tests will be sampled for the usability assessment across both study sites [15] [17]. As in the diagnostic performance assessment, the data from this usability assessment will be combined with data from a similar sample of health workers in other evaluations (a minimum of 15 in each Brazil and India) in order to reach the target number of users required by WHO PQ.

Participant group	Recruitment sample size	Target enrollment sample size
Participants	2,200	2,000
Health workers trained in the use of the G6PD test	18	15

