3.1 Statistical analyses

Data will be entered into a Microsoft Excel database with built-in validation rules to minimize data entry errors. Descriptive statistical analysis, including calculating point estimates, distribution, and frequencies of responses, will be used to summarize and characterize the study population.

3.1.1 Diagnostic accuracy and performance:

For the purposes of this study, an individual will be considered G6PD deficient (case) if they test positive by the spectrophotometric gold standard. The primary success criterion will be focused on the ability to identify G6PD deficient participants correctly, such that both the POC G6PD test and the spectrophotometric gold standard test should both accurately identify all G6PD deficient specimens (with < 20% normal) as deficient.

The performance of the POC G6PD against the spectrophotometric gold standard will be determined by calculating the sensitivity and specificity. Sensitivity and specificity of the SD Biosensor (SDB) G6PD assay were calculated as per Domingo et al. [14]. In summary, an adjusted male median will be calculated for both the POC G6PD and spectrophotometric gold standard test from where the 30%, 40%, 70% and 80% cutoff levels for the two tests will be used to categorically define G6PD deficient cases.

Sensitivity calculations will be determined by the following method: TTP=true and test positive (positive by reference assays according to case definition and positive by the POC G6PD test), FNTP=false negative true positive (positive by reference assays according to case definition and negative by the POC G6PD test). Sensitivity = $TTP/(TTP+FNTP)$.

Specificity will be determined by the following method: TPTN=test positive true negative (negative by reference assays according to case definition and positive by POC G6PD test), TTN=Test and true negative (negative by reference assays according to case definition and negative by POC G6PD test). Specificity= $TTN/(TTN+TPTN)$.

Sensitivity and specificity results will be reported using 95% confidence intervals.

3.1.2 Accuracy between G6PD activity and Hemoglobin methods:

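### The 95% sensitivity target is worded for 30-80% activity, but no planned sensitivity isolates that band, and the figure that is planned depends on the enriched case mix

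*Combined protocol and SAP*

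**What the plan says.** - **Target (Section 3.2).** Citing the target product profile, the plan says the test must be "at least 95% sensitive for detecting G6PD activity levels at 30% to 80% of normal enzyme activity". Table 2 in the same section defines the intermediate class, for females only, as "G6PD activity 30%-80% of the adjusted male median".
- **Sizing (Section 3.2).** The stated inputs are "Assuming a sensitivity of 95%, with a confidence interval of 95%, and a 1% to 2% maximum marginal error", and the result is "a minimum of 162 participants with deficient and intermediate G6PD activity will be needed". The denominator is now both classes together.
- **Numbers expected (Section 3.2).** The plan asks that "at least 200 participants of each group should be included in the study". It then says that in Brazil "testing a minimum of 2,000 individuals is expected to generate approximately 100 deficient and 200 intermediate individuals".
- **Analysis (Section 3.1.1).** Cases are defined at the "30%, 40%, 70% and 80% cutoff levels" of each test's adjusted male median. Sensitivity is the share of reference-positive participants who are also positive on the POC test. The primary success criterion concerns only specimens below 20% of normal.
- **Agreement (Section 3.1.2).** R-squared and Bland-Altman limits are planned across the range of activity. These are not classification measures.

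**The concern.** A case at the 70% or 80% cutoff is anyone whose reference activity lies below it, so both case groups contain everyone below 30%. The 30% case group contains no intermediates. None of the four planned sensitivities therefore has the denominator that the target names.

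Cases below 30% lie far from a 70% or 80% cutoff and should nearly all be detected there. Table 7 (Section 7.1) reports 100% sensitivity for them even at the 30% threshold. Adding them raises the pooled figure by an amount set by the ratio of deficient to intermediate participants. Enrichment and recruitment fix that ratio; the device does not.

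Section 1.0 says that qualitative tests cannot separate intermediate from normal activity, and that women need a quantitative test for this reason. Performance among intermediates is therefore a main question for this device, and the plan gives it no estimate of its own.

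**Working it through.** **1. The plan's own figure.** The usual precision formula is n = 1.96² × p(1 − p)/d², with p = 0.95.
- d = 0.02 gives 3.8415 × 0.0475/0.0004 = 457 (rounded up).
- d = 0.01 gives 1,825.
- The stated 162 is not reproduced. It gives a half-width of 1.96 × √(0.0475/162) = ±3.4 points. The nearest match found is d = 0.03, which gives n = 203, and 203 × 0.8 = 162, but the text does not state that margin.

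This is a separate matter. It is noted here because precision for intermediates has to be restated anyway.

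**2. Precision for intermediates alone, at 95%.**
- 200 in Brazil: 1.96 × √(0.0475/200) = ±3.0 points.
- 375 over the three countries in Section 3.2 (200 + 75 + 100): ±2.2 points.
- For comparison, 300 pooled in Brazil: ±2.5 points.

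**3. How far pooling can mask.** Let D be the number deficient, I the number intermediate and s the sensitivity among intermediates. Assume every case below 30% is detected. Pooled sensitivity is (D + sI)/(D + I). Setting it to 0.95 gives s = 1 − 0.05(D + I)/I.

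| Mix (D + I) | Source | s at which pooled = 95% |
|---|---|---|
| 100 + 200 | Brazil, expected | 92.5% |
| 188 + 375 | three countries, expected | 92.5% |
| 200 + 200 | minimum for each group | 90.0% |

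At 100 + 200, detecting 185 of 200 intermediates (92.5%, exact 95% CI 87.9 to 95.7) gives 285/300 = 95.0% pooled. Judged on the band alone, an observed 95% needs 190 of 200.

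**4. Chance of observing at least 95% (binomial, same assumption).**

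| Mix | True s | Pooled | Intermediates alone |
|---|---|---|---|
| 100 + 200 | 92.5% | 57% | 11% |
| 100 + 200 | 90% | 14% | 0.8% |
| 100 + 200 | 85% | 0.1% | <0.1% |
| 200 + 200 | 90% | 56% | 0.8% |

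At a true s of 80% and the 100 + 200 mix, expected pooled sensitivity is (100 + 160)/300 = 86.7%, and the chance of observing 95% is effectively zero.

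**5. Illustration from Table 7.** Its counts are not printed. Searching for counts whose exact limits match the printed intervals gives 73/73 or 74/74 at 30%, and 90/92 or 91/93 at 70%. Every case below 30% was positive at the POC threshold of 4.2, so it is also positive at 6.0, and the two misses in the 70% row lie at or above 30%. That leaves about 92 − 73 = 19 samples in the 30-70% band with 2 missed: 17/19 = 89% (exact 95% CI 67 to 99), against a pooled 98%.

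**The case against.** **The target may mean something else.** The target product profile is not in the documents. The sentence can be read as sensitivity at cutoffs from 30% to 80%. That reading fits the four cutoffs in Section 3.1.1 and the layout of Table 7, and it makes cumulative case groups natural. The literal wording and Table 2 favour the band, but the documents do not settle it. This stands, and it is why the plan should say which is meant.

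**No pass rule is at stake.** The 95% figure appears only in Section 3.2, as a requirement of the target product profile and a sizing assumption. This also stands. The risk lies in how the estimate is read against the target.

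**Intermediates are partly covered.** Section 3.2 sets a minimum for each group, Bland-Altman plots span the range, and band results might be approximated by subtracting one cumulative row from another. This stands in part. Subtraction is exact only if the number of cases below 30% detected at the higher POC cutoff is known. The cumulative cutoffs are also not sex-specific, whereas Table 2's intermediate class is female only.

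**Stronger readings.** A reader might infer that a test failing badly among intermediates could appear to meet 95%. Step 4 shows otherwise at the planned mixes. A reader might also take the 80% row of Table 7 as proof: its limits fit 92/104, which would leave 104 − 73 = 31 samples at 30-80% with 12 missed, or 19/31 = 61%. The documents do not support that use, for four reasons:
- The pooled figure in that row is already below 95%, so nothing is hidden.
- 92/104 = 88.5% disagrees with the printed 86%.
- The POC threshold rises from 6.0 to 6.2 between the 70% and 80% rows, so at most 2 samples below 70% can be missed at 6.2. At least 10 of the 12 misses therefore lie at 70-80%, next to the cutoff.
- The thresholds were chosen by ROC analysis, and the 314 data points span four ambient conditions, possibly with repeated specimens.

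**Conclusion.** The point holds as a gap in the estimand and the reporting, with a bounded effect. The target is worded for 30-80% activity, the sizing and the 70% and 80% sensitivities include all cases below 30%, and no planned sensitivity isolates intermediates. Pooling can credit the test with 95% when intermediate sensitivity is about 92.5 to 95% at the expected 1:2 mix, or 90 to 95% at 1:1.

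This rests on complete detection of cases below 30% and on the expected yields. If some of those cases were missed, the masking would be smaller. The Table 7 figure for the 30-70% band rests on back-calculated counts and about 19 laboratory samples. It illustrates the mechanism and does not predict the field result.

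**What to change.** **Section 3.1.1.** Keep the cumulative sensitivities and add:
- sensitivity with 95% CI for reference activity <30%, 30-70% and 30-80%, the two bands being for females as in Table 2;
- a definition of a hit: a POC result below the stratum's own upper cutoff, so below 70% or 80% of the POC adjusted male median for the two bands;
- a cross-table of POC class by reference class (deficient, intermediate, normal).

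**Section 3.2.** State whether the 95% target applies to the 30-80% band, as literally worded, or to the cumulative cutoffs. Compare the matching estimate with it. Give the expected precision for about 200 intermediates alone (about ±3.0 points at 95%).

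**Cost.** A few sentences and one extra table from data already being collected. The band intervals will be wider than the pooled ones, and the figure set against the target may be less favourable.

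### The 162 deficient and intermediate participants in Section 3.2 do not give the stated 1% to 2% margin; those inputs need 457 to 1,825, and 162 gives about ±3.4 points

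*Combined protocol and SAP*

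**What the plan says.** Section 3.2 (Sample size) of the combined protocol and SAP sets out the calculation in one sentence. It takes a sensitivity of 95% at 95% confidence and continues: "a 1% to 2% maximum marginal error, a minimum of 162 participants with deficient and intermediate G6PD activity will be needed". No formula or reference for the calculation is given, and the margin is not defined.

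The same section then adds 20% for device failures and compromised samples, and asks for at least 200 participants in each of the deficient and intermediate groups. For Brazil, it says that "testing a minimum of 2,000 individuals is expected to generate approximately 100 deficient and 200 intermediate individuals". The data are to be combined with those from Ethiopia ("expected to generate approximately 38 deficient and 75 intermediate individuals") and India ("expected to generate approximately 50 deficient and 100 intermediate individuals").

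Section 3.1.1 shows how the estimate will be presented: "Sensitivity and specificity results will be reported using 95% confidence intervals".

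**The concern.** The sentence supplies everything a precision calculation for one proportion needs: the expected proportion, the confidence level and the margin. It presents 162 as the outcome. A margin of 1 to 2 points around 95% requires several hundred cases at the least, so 162 looked too small. A single sample size attached to a range of margins was a further sign of trouble, because each margin has its own sample size.

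What is at stake is how precise readers expect the sensitivity estimate to be. The study is meant to support a WHO prequalification submission and product registration, and the sentence stands next to a target product profile requirement of at least 95% sensitivity. Someone relying on Section 3.2 would expect an interval much narrower than 162 cases, or Brazil's expected 300, can deliver.

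**Working it through.** **Inputs.** From Section 3.2: sensitivity p = 0.95, confidence 95%, margin d = 0.01 to 0.02, stated n = 162. Expected deficient plus intermediate cases: Brazil 100 + 200 = 300; Ethiopia 38 + 75 = 113; India 50 + 100 = 150; total 563. Sidedness is not stated; two-sided (z = 1.96) is taken, in line with the 95% intervals of Section 3.1.1.

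**Step 1: try to reproduce 162.** With n = z² p(1−p)/d² and p(1−p) = 0.95 × 0.05 = 0.0475:

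- d = 0.02: 1.96² × 0.0475 / 0.0004 = 456.2, so 457
- d = 0.01: 1.96² × 0.0475 / 0.0001 = 1,824.7, so 1,825

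The stated 162 is too small by a factor of 457/162 = 2.8 for the looser margin and 1,825/162 = 11.3 for the tighter one.

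**Step 2: try other readings.**

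| Reading | n at 2% | n at 1% |
|---|---|---|
| Two-sided Wald | 457 | 1,825 |
| One-sided 95% | 322 | 1,286 |
| Wilson half-width | 469 | 1,838 |
| Continuity-corrected | 505 | 1,924 |
| Exact (Clopper-Pearson) half-width | 508 | 1,927 |
| Margin read as one standard error | 119 | 475 |

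None gives 162. A finite population correction gives 162 at 2% only if the population is about 250, a figure that the documents do not contain. Using N = 2,000 gives 372.

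**Step 3: what 162 delivers.** The standard error is √(0.0475/162) = 1.71 points, and the 95% half-width is 1.96 × 1.71 = 3.36 points. As a check by another method, the exact interval for 154/162 (95.1%) runs from 90.5% to 97.8%, a half-width of 3.7 points.

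**Step 4: what the planned numbers deliver.** Half-width = 1.96 × √(0.0475/n):

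| Cases | n | Half-width (points) |
|---|---|---|
| Stated minimum | 162 | 3.4 |
| Two groups of 200 | 400 | 2.1 |
| Brazil, expected | 300 | 2.5 |
| Brazil, 300/1.2 | 250 | 2.7 |
| Brazil, 300 × 0.8 | 240 | 2.8 |
| Three countries, expected | 563 | 1.80 |
| Three countries, 563/1.2 | 469 | 1.97 |
| Three countries, 563 × 0.8 | 450 | 2.01 |
| Brazil, deficient only | 100 | 4.3 |
| Brazil, intermediate only | 200 | 3.0 |

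The rows with 1.2 and 0.8 are two ways of applying the protocol's 20% allowance to the expected counts. They are scenarios, not stated plans.

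**The case against.** The strongest defence is that the margin is undefined. The standard error at n = 162 is 1.71 points, which lies between 1% and 2%, so the author may have been describing a standard error. The sample size is also said to rest on WHO prequalification requirements and the target product profile, which are not reproduced in the protocol. This is possible but does not rescue the sentence. A standard error of exactly 1% or 2% gives 475 or 119, not 162, and on that reading the 95% confidence level would play no part in the calculation. What stands is that the origin of 162 is unknown, so the fix has to leave room for another definition.

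Second, 162 is overtaken within the section by the 20% increase, the 200-per-group minimum and pooling across countries. This is true, and it limits the consequences. But 400 cases still give ±2.1 points, Brazil expects 300 rather than 400, and pooling is introduced to reach WHO prequalification numbers, not to support the margin. The pool does come within 2% on expected counts.

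Third, the 20% allowance is applied in the protocol to the requirement, not to the 300 expected, and an invalid point-of-care result is repeated once. That is fair: the 240 to 250 figures for Brazil are illustrations only.

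Fourth, sensitivity will be estimated at separate cutoffs, and the primary success criterion concerns deficient specimens, so a combined figure flatters the precision. This also stands. Section 3.2 itself uses the combined group, but the half-widths for each group should be given beside it.

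**Conclusion.** The sentence is wrong as written. At 95% sensitivity and two-sided 95% confidence, a 1% to 2% margin requires 1,825 to 457 deficient and intermediate participants, and 162 gives about ±3.4 points. Brazil's expected 300 give about ±2.5 points, or up to 2.8 if 20% are not evaluable. The three-country total of 563 gives about ±1.8 points, or about 2.0 with the same loss. The 1% margin is out of reach in every case.

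This rests on reading the margin as a confidence interval half-width, which is the ordinary meaning, and on the expected counts in Section 3.2, which are approximate. The choice of interval method does not matter to the conclusion.

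The sentence should be corrected, but the error does not undermine the study. It affects the stated justification for precision and not the enrolment target, the analyses or any success criterion.

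**What to change.** In Section 3.2, state the formula that produced 162 and define the margin. Unless a different definition explains the figure, withdraw the 1% to 2% claim and restate the precision by one method with evaluable counts. Suggested wording:

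> By the Wald method at 95% sensitivity, 162 evaluable deficient and intermediate participants give a 95% confidence interval half-width of about 3.4 percentage points. The 300 expected in Brazil give about 2.5 (2.8 if 20% are not evaluable, n = 240). The 563 expected across Brazil, Ethiopia and India give about 1.8 (2.0 if 20% are not evaluable, n = 450). A margin of about 2% is expected only in the pooled analysis; a 1% margin is not reached. Taken separately, the 100 deficient and 200 intermediate participants expected in Brazil give about 4.3 and 3.0.

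If 162 came from another definition of margin, give that definition and its calculation instead.

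The cost is a few sentences. There is no extra enrolment and no change to the target of 2,000 or to any success criterion. The price is that the precision stated for Brazil alone becomes less favourable.

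### Section 3.2 asks for at least 200 deficient participants, but the plan's own projections give about 100 in Brazil and 188 pooled, and the two are not reconciled

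*Combined protocol and SAP*

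**What the plan says.** Section 3.2 first derives a combined minimum: "a minimum of 162 participants with deficient and intermediate G6PD activity will be needed". It allows a further 20% for device failures and compromised samples. As protection against low enrolment of the deficient and intermediate groups, it then adds that "at least 200 participants of each group should be included in the study". It continues: "This additional enriched sample will also serve to meet the requirements of the WHO PQ".

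The same section gives the projected yields:
- Brazil: "testing a minimum of 2,000 individuals is expected to generate approximately 100 deficient and 200 intermediate individuals".
- Ethiopia, from 1,500 tested: "expected to generate approximately 38 deficient and 75 intermediate individuals".
- India, from 1,000 tested: "expected to generate approximately 50 deficient and 100 intermediate individuals".

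It closes by saying that, with the data combined, "these studies will reach the target number of samples required by WHO PQ". The number that WHO PQ requires is not given.

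The synopsis (Population) repeats about 100 deficient, 200 intermediate and 1,700 normal for Brazil and bases these on estimated prevalence. Section 4.1 says that about half of participants will come from the stream with known G6PD status. The Figure 3 note and section 12.0 confirm that some enrichment or purposive sampling is intended. No section gives the expected number of deficient people in that stream. The inclusion criteria in section 4.2.2 require earlier survey participation and consent to re-contact, not a deficient or intermediate result.

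**The concern.** One section sets a floor of 200 for the deficient group and, a paragraph later, projects half that number for this study. Adding the two other countries still leaves the projection below the floor. The plan does not say whether the 200 refers to Brazil or to the pooled data, or whether it counts people enrolled or people with usable results.

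The effect falls mainly on sensitivity at the 30% cutoff, where deficient people are the only cases. At the 40%, 70% and 80% cutoffs they are only part of the cases. A sponsor setting recruitment quotas, or a reader judging the precision to expect at 30%, needs to know which number governs.

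**Working it through.** **1. Reproducing the plan's projections** (number tested × stated prevalence below 30% activity, section 3.2)
- Brazil: 2,000 × 5% = 100 (stated: 100).
- Ethiopia: 1,500 × 2.5% = 37.5 (stated: 38).
- India: 1,000 × 5% = 50 (stated: 50).

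All three reproduce. The Brazil figure is the prevalence applied to the whole 2,000, so it includes nothing for enrichment.

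**2. Projection against the floor of 200**
- Deficient, Brazil: 100 of 200.
- Deficient, pooled: 100 + 38 + 50 = 188 of 200, short by 12 (6%). The 188 is my sum and is not printed in the plan.
- Intermediate, Brazil: 200 of 200, with no slack.
- Intermediate, pooled: 200 + 75 + 100 = 375.

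Only the deficient group is affected.

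**3. What enrichment would have to supply**

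Assume 1,000 clinic participants at 5% deficient (50 people) and 1,000 known-status participants with deficient share *s*. The plan does not give *s*. Brazil's deficient count is then 50 + 1,000*s*, and the pooled count adds 38 + 50 = 88.
- *s* = 5%: 100 in Brazil, 188 pooled.
- *s* = 6.2%: 112 in Brazil, 200 pooled.
- *s* = 10%: 150 in Brazil, 238 pooled.
- *s* = 15%: 200 in Brazil, 288 pooled.

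**4. Precision at the 30% cutoff** (exact Clopper-Pearson 95% intervals, observed sensitivity at or near 95%)
- 95/100: 88.7% to 98.4%.
- 190/200: 91.0% to 97.6%. The lower limit differs from that with 100 by 2.3 points.
- After a 20% loss, 76/80: 87.7% to 98.6%; 152/160: 90.4% to 97.8%. The lower limits differ by 2.7 points.
- Pooled, 188 (95% is not a whole number): 178/188 gives a lower limit of 90.4% and 179/188 gives 91.1%, against 91.0% with 200.
- Pooled after a 20% loss: 142/150 gives 89.8% and 143/150 gives 90.6%, against 90.4% with 160.

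**5. Enrolled or evaluable**

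If 200 must remain after a 20% loss, 200 / 0.8 = 250 must be enrolled in each group. In Brazil this affects intermediates too, since 200 × 0.8 = 160. Pooled, 375 × 0.8 = 300, so intermediates still meet the floor.

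**6. The 162 gives no reassurance**

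Brazil's projected 300 deficient plus intermediate is above 162 × 1.2 = 194.4, but the 162 does not follow from its own inputs. With n = 1.96² × 0.95 × 0.05 / d², a margin of d = 2 points needs 457 and d = 1 point needs 1,825. At n = 162 the half-width is 1.96 × √(0.0475/162) = 3.4 points, and at n = 300 it is 2.5 points.

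**The case against.** The best answer on the plan's behalf has four parts.

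- **The two numbers may differ in kind.** The 100 is a prevalence projection and the 200 an enrichment target, and both can be true. A deficient share of 6.2% in the known-status half, barely above the 5% background, brings the pooled count to 200. This stands as far as it goes, and it is why a reader should not infer that the study will fall short of 200. However, the synopsis gives 100 for the whole Brazil sample, which already includes the enriched half, and no yield or quota links the two figures.
- **The data are to be pooled.** Section 3.2 says so, and 188 against 200 is a small gap between approximate figures. This also stands: on that reading the precision loss is negligible and only a restatement is needed. But the sentence setting the 200 does not say that it is pooled, and the pooled projection is still below it.
- **No stated threshold is crossed.** The plan sizes precision on deficient and intermediate participants together and sets no requirement for deficient participants alone, so 88.7% against 91.0% breaches nothing in the text. This is correct.
- **The Brazil projection is consistent.** The synopsis and section 3.2 agree on about 100. What is unclear is the scope of the 200 and how it is to be reached.

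Two stronger readings are tempting and unsupported. One is that the primary success criterion loses precision by the amounts above. That criterion concerns specimens below 20% of normal, a subset whose size is not given, so these intervals do not describe it. The other is that the WHO PQ requirement will not be met. The plan does not state that number, so the documents cannot settle it either way.

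**Conclusion.** The inconsistency is real and limited to the deficient group. The plan states a floor of 200 and projects 100 in Brazil or 188 pooled, so the projection does not deliver the floor on either reading. On the Brazil reading, the lower limit for sensitivity at the 30% cutoff is 2.3 points worse than the floor implies (2.7 points after a 20% loss). On the pooled reading the gap is 6% with no material loss of precision.

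The projections rest on the plan's own prevalences, and the intervals assume an observed sensitivity at or near 95%. The enrichment range also assumes an even split between streams and 5% deficient in the clinic stream. This should be fixed because the correction is cheap, but it does not show that the study will fail.

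**What to change.** Keep the total at 2,000 and make these changes in section 3.2 and the synopsis:

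1. State whether the 200 applies to Brazil or to the pooled data, and whether it counts enrolled or evaluable participants.
2. Give expected deficient, intermediate and normal counts separately for the clinic and household streams, with the precision that follows for the deficient group.
3. Then choose one of two routes:
   - **Restate the target.** Set the deficient target at the projected number (about 100 in Brazil, 188 pooled) with its precision, after checking that the cited WHO PQ requirement allows it.
   - **Keep the 200 through a quota.** If the register of earlier survey participants holds enough reachable known-deficient people, set a quota in the household stream. With 5% in 1,000 clinic participants, that is 200 − 50 = 150 for 200 enrolled in Brazil (normals fall from 1,700 to 2,000 − 400 = 1,600), or 200 − 88 − 50 = 62 for 200 pooled.
4. If the 200 must be evaluable after a 20% loss, plan for 250 enrolled in each group. The deficient quotas become 250 − 50 = 200 for Brazil or 250 − 88 − 50 = 112 pooled. On the Brazil reading, 50 more intermediates than projected are also needed and normals fall to 2,000 − 500 = 1,500. On the pooled reading the intermediates need no change.
5. Do not use the 162 to justify any of these numbers until it has been re-derived from its stated inputs.

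Restating costs some wording and one small table, and the stated figure becomes less favourable. A quota adds recruitment work from an existing list whose contents the documents do not give, and makes the household stream more selected.
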